9.4 Statistical Methods

All data collected in the clinical database will be presented in subject data listings.

Unless otherwise specified, baseline value for each parameter will be defined as the last available assessment prior to the first dose of the study treatment.

No adjustment for covariates will be included in the primary analysis of the primary endpoint or the analysis of the secondary and other endpoints that are binary in nature. Analyses of the continuous efficacy endpoints will be adjusted for baseline values of the corresponding parameters.

Data collected after the initiation of rescue medication (as described in Section 6.13.3) will be used in all main analyses.

The primary endpoint as well as secondary and other endpoints that are binary in nature will be analyzed using a 2×2 chi-squared test for equality of proportions for each OKZ treatment group compared with placebo.

Endpoints that are continuous in nature will be analyzed using an analysis of covariance (ANCOVA) model adjusted for the baseline value of the corresponding parameter.

Continuous efficacy endpoints will be summarized using descriptive statistics such number of available values (n), mean, median, minimum, maximum, and standard deviation for the 3 treatment groups, respectively. Categorical efficacy endpoints will be summarized by the number and percentage of subjects in each category.

Efficacy analyses will be conducted using the ITT population. Supportive analyses of the primary and secondary efficacy endpoints will be conducted using the mITT (if sufficiently different from the ITT population) and PP populations. All comparisons for efficacy assessments will be carried out based on treatment groups to which the subjects were originally randomized.

Safety analyses will be done according to the treatment subjects actually received.

Details for the statistical analysis will be specified in the Statistical Analysis Plan (SAP) to be written and finalized prior to the unblinding of the database. The statistical analysis will be performed by R-Pharm's designee.

All statistical analyses will be conducted using SAS[®] version 9.2 or higher for Windows.

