The references cited above for ACR20 and DAS28 response rates are assumed to reflect approximately 10% of subjects discontinuing randomized treatment prior to Week 12. In this study, subjects who discontinue prior to Week 12 will be classified as nonresponders for the primary endpoint of ACR20 at Week 12 as well as for the secondary endpoint of DAS28 (CRP) <3.2 at Week 12.

The primary endpoint as well as the secondary endpoints that are binary in nature will be analyzed using a 2x2 chi-squared test for equality of proportions for each OKZ treatment group compared with placebo.

Based on the treatment effect assumptions and the methodology for estimating sample size via simulation to ensure sufficient disjunctive power as described above, a sample size of 420 subjects randomized in a 1:1:1 ratio (140 subjects per treatment group) will yield 100% disjunctive power for testing the primary hypothesis (ACR20 at Week 12) and 98% disjunctive power for the evaluation of the secondary endpoint of DAS28 (CRP) <3.2 rate at Week 12.

Analysis Populations

- Intent-to-treat (ITT) population: The ITT population will include all randomized subjects. Subjects will be analyzed according to the treatment group to which they were randomized. The ITT population will be the primary analysis population.
- Modified Intent-to-treat (mITT) population: The mITT population will include all randomized subjects who receive at least 1 dose of study treatment. Subjects will be analyzed according to the treatment group to which they were randomized. The mITT population, if sufficiently different from the ITT population (>5% of ITT subjects excluded from mITT across all treatment groups), will be used for supportive analyses of the primary and secondary efficacy endpoints.
- Per Protocol (PP) population: The PP population will include all ITT subjects who do not have any major protocol violations. Subjects will be analyzed according to the treatment group to which they were randomized. Major protocol violations and the inclusion of subjects in the PP population will be finalized prior to study unblinding. The PP population will be used for supportive analyses of the primary and secondary efficacy endpoints.

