The ACR20 response rate at Week 12 for the placebo group is estimated to be 25% in this study population (Genovese et al, 2008; Keystone et al, 2004; Weinblatt et al, 2003). The OKZ ACR20 response rates for 64 mg q4w and q2w treatment groups at Week 12 are expected to be at least 50% and 55% respectively, resulting in an expected difference in ACR20 response rates of 25 and 30 percentage points between respective OKZ treatment groups and placebo.

The DAS28 low disease activity (based on DAS28 [CRP] <3.2) response rate at Week 12 is estimated to be 10% in the placebo group (van der Heijde et al, 2006) and 22% and 30% in 64 mg q4w and q2w OKZ treatment groups respectively, resulting in an expected difference of 12 and 20 percentage points between respective OKZ treatment groups and placebo.

The references cited above for ACR20 and DAS28 response rates are assumed to reflect approximately 10% of subjects discontinuing randomized treatment prior to Week 12. In this study, subjects who discontinue prior to Week 12 will be classified as nonresponders for the primary endpoint of ACR20 at Week 12 as well as for the secondary endpoint of DAS28 (CRP) <3.2 at Week 12.

The primary endpoint as well as the secondary endpoints that are binary in nature will be analyzed using a 2×2 chi-squared test for equality of proportions for each OKZ treatment group compared with placebo.

Based on the treatment effect assumptions and the methodology for estimating sample size via simulation to ensure sufficient disjunctive power as described above, a sample size of 420 subjects randomized in a 1:1:1 ratio (140 subjects per treatment group) will yield 100% disjunctive power for testing the primary hypothesis (ACR20 at Week 12) and 98% disjunctive power for the evaluation of the secondary endpoint of DAS28 (CRP) <3.2 rate at Week 12.

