9.4.7 Primary Efficacy Analysis

The primary efficacy endpoint is the percentage of subjects achieving an ACR20 response and remaining on randomized treatment and in the study at Week 12, analyzed using the ITT population as the primary efficacy analysis. Supportive analyses of the primary endpoint will also be done using the mITT, if sufficiently different from the ITT population, and PP populations.

The ACR20 response at Week 12 for each of the OKZ 64 mg treatment groups (q2w and q4w) will be compared with placebo using a 2×2 chi-squared test for equality of proportions.

The overall Type I error rate will be controlled using a procedure in the strong sense at a 1-sided $\alpha = 0.025$ for testing multiple hypotheses for the 2 OKZ treatment groups versus placebo across the primary and secondary endpoints as described in Section 9.4.6.

As a supportive analysis, the difference between proportions of responders in each of the OKZ treatment groups and placebo (relative risk) will be estimated together with the corresponding 97.5% 2-sided confidence interval for difference of proportions using the Newcombe hybrid score method.

Missing data and data collected post premature study treatment discontinuation will be handled as described in Section 9.4.9.1.

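### DAS28 (CRP) <3.2 at Week 12, the first gated secondary, is tested without baseline adjustment: a modest efficiency loss, mainly for q4w, not an error

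*Combined protocol and SAP*

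**What the plan says.** - **Binary endpoints.** Section 9.4 says "No adjustment for covariates will be included in the primary analysis of the primary endpoint or the analysis of the secondary and other endpoints"; the sentence goes on to restrict this to binary endpoints. The Synopsis (Efficacy Analysis) repeats it. The Synopsis (Calculation of Sample Size) adds that "the secondary endpoints that are binary in nature will be analyzed using a 2x2 chi-squared test for equality of proportions". Sections 9.1 and 9.4.8 agree.
- **Continuous endpoints.** Section 9.4: "Analyses of the continuous efficacy endpoints will be adjusted for baseline values of the corresponding parameters". Baseline is defined there too: "baseline value for each parameter will be defined as the last available assessment prior to the first dose of the study treatment".
- **Role of the endpoint.** DAS28 (CRP) <3.2 at Week 12 comes first in Section 4.2. Under Section 9.4.6 each regimen is tested in fixed order at one-sided 0.0125 and stops at its first non-significant result. HAQ-DI, ACR50 and CDAI ≤2.8 follow.
- **Baseline data.** Section 7.1.6 builds the score from tender and swollen 28-joint counts, CRP and patient global assessment. Section 5.4.1.2 schedules all of these before the first dose. Section 4.3 already needs baseline DAS28 (CRP) for a change-from-baseline endpoint.
- **Power.** Section 9.1 assumes 10% on placebo "and 22% and 30% in 64 mg q4w and q2w OKZ treatment groups respectively", and states "98% disjunctive power for the evaluation of the secondary endpoint of DAS28 (CRP) <3.2 rate at Week 12".
- **Interval.** Section 9.4.7 gives a "97.5% 2-sided confidence interval for difference of proportions using the Newcombe hybrid score method".

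**The concern.** The endpoint is an absolute cut-off on a score that is also measured at baseline. Where a subject starts may well predict whether the cut-off is reached, and the plan uses that information for continuous endpoints but not here. ACR20 and ACR50 differ, because they are defined as percentage improvement from baseline.

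The stake is the gate. If q4w misses significance on this test, its HAQ-DI, ACR50 and CDAI hypotheses are not tested. q2w follows its own sequence and is unaffected. None of the sensitivity analyses in Section 9.4.9.2 adjusts this endpoint for baseline.

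**Working it through.** **Inputs from the documents.** 140 per arm; one-sided alpha 0.0125 per regimen (z = 2.2414); DAS28 (CRP) <3.2 rates of 10%, 22% (q4w) and 30% (q2w); ACR20 rates of 25%, 50% and 55%; about 10% discontinuing before Week 12, counted as nonresponders and already reflected in the rates (Sections 9.1 and 9.4.6).

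**Assumed.** The correlation between baseline DAS28 (CRP) and the latent Week 12 score is not in the documents; 0 to 0.6 is used.

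**Step 1. Unadjusted power per regimen.** Power = Φ{[δ√n − z√(2p̄(1−p̄))] / √(p0(1−p0)+p1(1−p1))}.
- q4w: (0.12×11.832 − 2.2414×0.5185)/0.5115 = 0.504, giving 69.3%.
- q2w: (0.20×11.832 − 2.2414×0.5657)/0.5477 = 2.006, giving 97.8%.

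**Step 2. The plan's own figures.** Simulating the Bonferroni and gate-keeping procedure (40,000 trials, shared placebo arm, ACR20-DAS28 correlation 0 to 0.9) gives disjunctive power of 98.5-98.6% for DAS28 (stated 98%) and 99.9-100% for ACR20 (stated 100%). Both reproduce. The 98% is carried almost entirely by q2w.

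**Step 3. q4w power with adjustment.** Logistic model with treatment and baseline, standardised to the risk difference, robust SE, t reference with 280 − 3 = 277 df. Each cell is unadjusted / adjusted, in %.

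| Assumed correlation | Run 1 | Run 2 | Run 3 | Gain (points) |
|---|---|---|---|---|
| 0 | 71.3 / 71.1 | 69.7 / 69.3 | 70.1 / 69.8 | about 0 |
| 0.3 | 71.3 / 72.4 | 71.5 / 72.8 | 70.8 / 72.6 | 1-2 |
| 0.5 | 70.6 / 76.1 | 70.1 / 75.8 | 70.9 / 75.7 | 5-6 |
| 0.6 | 70.0 / 77.7 | 70.9 / 78.3 | 70.8 / 79.1 | 7-8 |

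Run 1 used 10,000 trials and 10% random dropout counted as nonresponse.

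**Step 4. Closed-form cross-check.** With dropout, the simulated variance ratios (adjusted/unadjusted) were 0.97, 0.89 and 0.85 at 0.3, 0.5 and 0.6. Unadjusted, δ√n/σ = 1.4199/0.5115 = 2.776. Φ(2.776/√ratio − 2.2414) gives 71.8%, 75.8% and 77.9%, in line with Step 3. In sample-size terms, 140/ratio = 144, 157 and 165 per arm.

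**Step 5. Study-level effect.** Disjunctive power rises from about 98.5% to 98.9%, 99.4% and 99.6% at 0.3, 0.5 and 0.6 (likelihood-ratio version of the adjusted test). In a separate gated run (normal reference, ACR20 assumed independent of DAS28), the chance that q4w passes both ACR20 and DAS28, and so reaches HAQ-DI, went from 69-70% to 69%, 70%, 75% and 77% at 0, 0.3, 0.5 and 0.6.

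**Step 6. Validity of the alternative.** Over 15 null settings (40,000 trials each), mean one-sided rejection was 1.27% for chi-squared and 1.28% for the adjusted test with t reference (nominal 1.25%); a normal reference gave 1.32%. With the t reference, null rejection stayed at 1.2-1.3%, including with 5% of baselines mean-imputed. Non-convergence was below 0.01% of fits. Expected placebo responders are 140×0.10 = 14, and P(fewer than 5) = 0.12%.

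**The case against.** **No defect is shown, and the design target is met.** The chi-squared test is valid under randomization, is stated consistently, and is the test that was powered. Section 6.5 names no stratification factor that the analysis ignores. The planned criterion is disjunctive power, which barely moves. All of this stands and caps the point at a suggestion.

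**The gain rests on an unknown correlation.** True. At 0 nothing is gained, and at 0.3 only 1-2 points. But at 0 the cost in power is within simulation error.

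**A supportive adjusted analysis would do.** Section 9.4.9.2 allows further sensitivity analyses in the SAP, and this is a reasonable lesser step. It recovers no power, though, because Section 9.4.6 applies the gate only to the primary analysis of each endpoint.

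**Singling out one endpoint is arbitrary.** CDAI ≤2.8 is also an absolute cut-off. It is last in the sequence, so it gates nothing, and the plan gives no assumed CDAI rates from which to size a gain. The loss of uniformity is nevertheless a real cost.

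**Eligibility restricts the baseline range.** A reader might infer a floor: six tender and six swollen joints, CRP at an assumed upper limit of 3-10 mg/L and patient global 0 give 0.84×√6 + 0.36×ln(CRP+1) + 0.96 = 3.5-3.9. The documents do not support this. Section 5.3.1 counts 68 and 66 joints, and all six may lie outside the 28-joint set (distal finger joints, ankles and toes, for example). On the same CRP values the score is then 0.96 + 0.36×ln(CRP+1) = 1.5-1.8. CRP above the limit is also required only at Screening. If the range were restricted, the gain would shrink: with an assumed floor at −1 SD it is about 2 points at correlation 0.5.

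**Conclusion.** The point holds as an efficiency loss worth considering, with medium confidence. It concerns one endpoint and chiefly one regimen: about 0, 1-2, 5-6 and 7-8 points of q4w power at assumed correlations of 0, 0.3, 0.5 and 0.6, and at most about 1 point of disjunctive power.

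Two stronger readings should be resisted. A reader might infer that the chi-squared test is wrong or the trial underpowered; its type I error is correct and the 98% reproduces. A reader might also infer that the missing adjustment causes q4w's 70%. It does not: that figure follows from 10% versus 22%, 140 per arm and one-sided 0.0125. Even at correlation 0.6 adjustment lifts it only to about 78%, so it is a partial remedy.

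The size depends on the plan's response rates, the assumed correlation, and dropout unrelated to baseline.

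**What to change.** Before unblinding, amend the Synopsis (Calculation of Sample Size; Efficacy Analysis) and Sections 9.1, 9.4, 9.4.7 and 9.4.8, for DAS28 (CRP) <3.2 at Week 12 only:

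- **Main analysis.** Logistic model with treatment and baseline DAS28 (CRP), fitted to the two compared arms and standardised to the marginal risk difference. Robust SE, t reference with N−3 df, one-sided 0.0125, matching 97.5% two-sided interval.
- **Missing baseline score.** Impute the overall baseline mean, so that every ITT subject is kept.
- **Sensitivity analysis and fallback.** Chi-squared with the Newcombe interval, also used if the model does not converge.
- **Other analyses of this endpoint.** Use the adjusted method for mITT, PP, the treatment-discontinuation supportive analysis and the multiple-imputation analysis (combining the standardised difference and SE by Rubin's rule). Leave the count-based tipping-point analysis in Section 9.4.9.2 on chi-squared, and say so.
- **Unchanged.** ACR20, ACR50, CDAI ≤2.8, and DAS28 (CRP) <3.2 at other visits.

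**Cost.** Wording and modest programming; no new data. The main test would no longer exactly match the sample-size method, and the tipping-point analysis would use a different test from the main one. The current amendment covers only Russia and Belarus (Appendix 8), so the change must be aligned across all participating countries.

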9.4.1 Disposition of Study Subjects

Disposition of study subjects will be summarized by treatment group as the number and percentage of subjects screened (signed ICF), randomized, included in each analysis population as defined in Section 9.3, completing the study treatment, discontinuing from the study treatment overall and by reason for discontinuation, completing the study, discontinuing from the study overall and by reason for discontinuation, and enrolling into the OLE study. The number and percentage of subjects discontinuing study treatment by visit in each treatment group will also be summarized. A Kaplan-Meier plot of time to treatment discontinuation in each treatment group will be presented.

Determination of major protocol deviations and inclusion of subjects in the analysis populations will be finalized and approved by R-Pharm prior to the study unblinding.

9.4.2 Demography and Baseline Characteristics

Demographic information, baseline characteristics, and prior and concomitant medications will be presented using descriptive statistics or frequency counts, as appropriate, for continuous and categorical variables.

9.4.3 Medical History

A complete medical history will include evaluation (past or present) of the following: general, head and neck, eyes, ears, nose, throat, chest/respiratory, CV, GI/liver, gynecological/urogenital, musculoskeletal/extremities, skin, neurological/psychiatric,

endocrine/metabolic, hematologic/lymphatic, allergies/drug sensitivities, past surgeries, substance abuse, or any other diseases or disorders. Medical history terms will be coded using the most recent version of the MedDRA, listed by subject, and summarized by SOC and PT in each treatment group.

9.4.4 Prior and Concomitant Medications

Prior and concomitant medications will be separately summarized as the number and percentage of subjects by World Health Organization (WHO) drug class, preferred name, and treatment. Medications will be coded using the WHO Drug dictionary, Anatomic Therapeutic Class (ATC) level 2, and preferred drug name.

Prior medications will be distinguished from concomitant medications by a stop date before the first dose of the study treatment. Medications that stopped on the same date as the first dose of the study treatment will be considered a prior medication. Any medication that a subject started before the first dose of double-blind study treatment and continued to take during the study, and any medication that the subject began taking after the first dose of study treatment will be classified as concomitant.

Medications administered as rescue medication (as described in Section 6.13.3) will also be summarized as the number and percentage of subjects by WHO drug class, preferred name, and treatment.

9.4.5 Exposure and Compliance

Exposure to study treatment and compliance will be summarized descriptively by treatment group for the Safety population.

Exposure to double-blind study treatment will be calculated as the number of doses received in the course of the study. Duration of exposure will be defined as the total number of days a subject was exposed to study treatment, calculated as:

Date of last dose – Date of first dose + 1 day.

Overall compliance (expressed as a percentage) will be calculated as:

(Exposure to double-blind study treatment / Number of doses subject was expected to receive) × 100.

Duration of exposure and compliance will be calculated based on all planned doses (placebo and active treatment), as appropriate for each treatment group. For the OKZ 64 mg q4w dosing regimen, both OKZ and placebo doses will be used in the calculations.

9.4.6 Multiple Hypothesis Testing

Each of the OKZ treatment groups (64 mg q2w and q4w) will be compared with placebo for each of the primary, secondary, and other endpoints. The overall Type I error rate will be controlled for testing hypotheses of the primary and secondary endpoints at the overall 1-sided $\alpha = 0.025$. The α -control strategy will be based on using the Bonferroni adjustment for the tests related to each of the 2 OKZ dose regimens versus placebo (i.e., using the 1-sided $\alpha = 0.0125$ for each dose). A gate-keeping strategy will be used for tests associated with the primary and secondary endpoints for each OKZ dose regimen independently with the same order of testing as the secondary endpoints are defined above. In other words, each OKZ dose regimen will be tested at 1-sided $\alpha = 0.0125$ for a given endpoint if null hypotheses are rejected at 1-sided $\alpha = 0.0125$ for this dosing regimen for all previous endpoints based on the established order. Conversely, the testing will stop for a given OKZ dose regimen at the endpoint for which the null hypothesis is accepted at 1-sided $\alpha = 0.0125$.

The above multiplicity control procedure will be applied to the primary analysis of the primary and secondary efficacy endpoints based on the ITT population, and will not be applied to sensitivity analyses of these endpoints.

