Due to an increase in the concentration of the formulation subsequent to Phase II, it should be noted that the lowest volume which can be used in Phase III (0.4 mL) results in a nominal dose of 64 mg rather than 60 mg.

Consequently, using the primary efficacy outcomes from individual Phase II studies, and additional dose-response analysis performed on a combined database derived from these studies, 2 OKZ dose regimens were selected for further investigation: 64 mg SC q2w and 64 mg SC q4w since totality of the data strongly suggested that both of these dose regimens could potentially be successful in a large Phase III program.

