9. STATISTICS

9.1 Determination of Sample Size

Given that the study would be considered successful if at least 1 of the 2 OKZ dose regimens is shown to be efficacious and that a priori both OKZ dose regimens are assumed to be efficacious, we are using disjunctive power (i.e., a probability of detecting a significant treatment effect for at least 1 OKZ treatment regimen), as a criterion for the estimation of the sample size. Sample size requirements are calculated to provide sufficient disjunctive power to evaluate the primary endpoint (ACR20 response rate at Week 12) and the first secondary endpoint (DAS28 [CRP] <3.2 at Week 12). Sample size was estimated taking into account a multiplicity control procedure and the resulting α adjustment that will be used in this study to control an overall Type I error rate in the strong sense at a 1-sided $\alpha = 0.025$ across the primary and secondary endpoints. More specifically, the α -control strategy will be based on using the Bonferroni adjustment for the tests related to each of the 2 OKZ dose regimens versus placebo (i.e., using the 1-sided $\alpha = 0.0125$ for each dose). A gate-keeping strategy will be used for tests associated with the primary and secondary endpoints for each OKZ dose regimen independently, with a fixed order of hypothesis tests for the primary and secondary endpoints within each OKZ dose regimen. Sample size was estimated based on simulation that implemented the above α adjustment and gate-keeping procedure including the primary endpoint of ACR20 response rate at Week 12 and the first secondary endpoint. Based on this simulation, an adequate sample size was selected to provide sufficient disjunctive power for the primary endpoint and the first secondary endpoint based on DAS28 (CRP) <3.2 rate at Week 12. For the first secondary endpoint, the disjunctive power represents a probability of establishing a significant treatment effect for 1 or 2 OKZ dose regimens for the primary endpoint and a significant treatment effect for 1 or 2 OKZ dose regimens for the first secondary endpoint, conditional on the fact that each dose regimen tested for the secondary endpoint must have null hypothesis previously rejected for the primary endpoint based on a fixed order of testing as per the gate-keeping procedure.

Treatment effect assumptions used in the simulation-based sample size calculations, involving the primary and the first secondary endpoint are as follows.

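### The multiplicity plan is valid, but it leaves a completed regimen's one-sided 0.0125 unused; passing it on would lift q4w power for DAS28 (CRP) <3.2 from about 70% to somewhere between 70% and 79%

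*Combined protocol and SAP*

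**What the plan says.** Section 9.4.6, repeated in the synopsis, splits the overall one-sided 0.025 by Bonferroni into 0.0125 for each regimen. It continues: "A gate-keeping strategy will be used for tests associated with the primary and secondary endpoints for each OKZ dose regimen independently". The order is ACR20 at Week 12, DAS28 (CRP) <3.2 at Week 12, HAQ-DI at Week 12, ACR50 at Week 24 and CDAI remission at Week 24 (Sections 4.1 and 4.2). A regimen stops at its first non-rejection. Nothing transfers alpha between regimens.

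Section 9.1 explains the choice of disjunctive power: "the study would be considered successful if at least 1 of the 2 OKZ dose regimens is shown to be efficacious". It reports 100% for ACR20 and "98% disjunctive power for the evaluation of the secondary endpoint of DAS28 (CRP) <3.2 rate at Week 12". The assumed DAS28 rates are 10% on placebo and "22% and 30% in 64 mg q4w and q2w OKZ treatment groups respectively". Power for each regimen separately is not given.

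Section 9.4.7 pairs the tests with a "97.5% 2-sided confidence interval for difference of proportions using the Newcombe hybrid score method".

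**The concern.** Running the two sequences independently means that a regimen which wins everything cannot help the other. That matters for q4w, the weaker regimen in the planning assumptions. A q4w miss on DAS28, about a 30% chance on the plan's own rates, also ends formal q4w testing of HAQ-DI, ACR50 and CDAI remission.

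The primary claim for q4w is not at risk, since its ACR20 power is about 98%. What is at stake is the set of q4w secondary claims. Section 2.2.4 indicates that the sponsor has an interest in both regimens: "totality of the data strongly suggested that both of these dose regimens could potentially be successful in a large Phase III program". Because only disjunctive power is reported, a reader of Section 9.1 cannot see how the regimens differ.

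**Working it through.** **Inputs (Sections 9.1 and 9.4.6).** 140 per arm; ACR20 25% on placebo, 50% on q4w, 55% on q2w; DAS28 <3.2 10%, 22%, 30%; 2×2 chi-squared test; one-sided 0.0125 per regimen. The 10% discontinuation before Week 12 is already in the rates.

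**1. The plan's own figures reproduce.** Simulating the three arms with a shared placebo group and the gate (400,000 trials, ACR20 and DAS28 either independent or nested within subject) gives disjunctive power of 99.97% for ACR20 (stated 100%) and 98.5% for DAS28 (stated 98%).

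**2. Power by regimen.** Power = Φ[(d − z·s0)/s1], with s0 = √(2·p̄(1−p̄)/n) and s1 = √((p0(1−p0) + p1(1−p1))/n).

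For q4w on DAS28: d = 0.12, p̄ = 0.16, s0 = √(0.2688/140) = 0.04382, s1 = √(0.2616/140) = 0.04323.

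- At 0.0125: (0.12 − 2.2414 × 0.04382)/0.04323 = 0.504, power 69.3%.
- At 0.025: (0.12 − 1.9600 × 0.04382)/0.04323 = 0.789, power 78.5%.

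| Comparison | Formula, 0.0125 | Exact binomial, 0.0125 | Exact binomial, 0.025 |
|---|---|---|---|
| ACR20 q4w | 98.4% | 98.4% | 99.3% |
| ACR20 q2w | 99.9% | 99.9% | 99.95% |
| DAS28 q4w | 69.3% | 70.6% | 79.5% |
| DAS28 q2w | 97.8% | 98.1% | 99.1% |

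With the ACR20 gate, q4w DAS28 power at 0.0125 is 69.5% (independent) to 70.3% (nested). The reported 98% therefore comes from q2w.

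**3. Where the shortfall comes from.** For 80% power, n per arm = [(z·√(2p̄(1−p̄)) + 0.8416·√(p0(1−p0) + p1(1−p1)))/d]².

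- At 0.0125: (1.1621 + 0.4305)/0.12 = 13.27, squared 176.1, so 177.
- At 0.025: (1.0162 + 0.4305)/0.12 = 12.06, squared 145.3, so 146.

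Even the full 0.025 falls just short at 140 per arm. Effect size and sample size explain most of the gap to the power on ACR20.

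**4. Gain from passing alpha.** q4w moves to 0.025 only if q2w rejects all five hypotheses.

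| Probability that q2w wins HAQ-DI, ACR50 and CDAI, given wins on the first two | q4w DAS28 power |
|---|---|
| 0 (current plan) | 69.5–70.3% |
| 0.25 | 71.8–72.5% |
| 0.50 | 74.1–74.7% |
| 0.75 | 76.4–76.8% |
| 1 | 78.7–79.1% |

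The documents give no effects for these three endpoints. A five-endpoint simulation (20,000 trials per scenario, endpoint correlation 0.3 and 0.6) used assumed values: HAQ-DI effect 0.45–0.5 SD, ACR50 10% versus 25–30%, and placebo CDAI remission 3%. With q2w CDAI remission of 3%, 8%, 10% or 15%, q2w completes its sequence in about 1%, 32–33%, 54–55% or 88% of trials. q4w DAS28 power rises by 0.1, 2.5–3.0, 4.7 or 8.1 points.

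**5. Error control with passing.** If both sequences contain a true null, neither can be completed without an error having already occurred, so the first error arises at 0.0125 in one or other sequence: at most 0.0125 + 0.0125 = 0.025. If only one sequence contains true nulls, its first true null is tested at 0.025 at most. Simulated family-wise error in five null configurations (400,000 runs each) was 0.0230, 0.0249, 0.0249, 0.0231 and 0.0246. No rejection was lost relative to the current plan.

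**6. Intervals.** q4w DAS28 results with one-sided p between 0.0125 and 0.025 occur in 8.9% of trials. In all of these the 97.5% Newcombe interval includes zero; in 7.3% of them the 95% interval does too, because it does not exactly invert the chi-squared test.

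**The case against.** The plan is valid, defines success as at least one efficacious regimen, and reaches that target. Nothing in the documents makes a formal q4w secondary claim a design requirement; the remark in Section 2.2.4 is dose-selection rationale. This stands, and it is why the point is one of efficiency.

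The gain is also uncertain, and the scenarios above hold placebo CDAI remission at 3%. Week 14 nonresponders in every arm receive rescue medication (Section 6.13.3) and post-rescue data enter the main analyses (Section 9.4), so Week 24 placebo response could be higher. With q2w remission of 8%, 10% or 15%, exact q2w power for CDAI alone at 0.0125 is 34%, 57% or 93% against 3% on placebo, 11%, 25% or 73% against an assumed 5%, and 1%, 5% or 35% against an assumed 8%. These figures cap how often q2w completes its sequence. Multiplying by about 9 points gives gains of roughly 1, 2 and 7 points at 5%, and roughly 0 to 3 at 8%. This also stands, but it only moves the answer within the 0 to 9 range.

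Finally, passing alpha makes a Week 12 q4w claim depend on a Week 24 q2w result and brings in a second interval level. That is a real reporting cost. It calls for a stated interval rule, and it takes away no claim that the current plan would allow.

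**Conclusion.** The concern holds as an improvement to a valid plan. On the plan's own assumptions, q4w has about 70% power for DAS28 (CRP) <3.2. Passing on a completed regimen's alpha raises this by 0 to about 9 points, with strong control at one-sided 0.025 kept.

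The 70% and the 79% ceiling rest on the Section 9.1 rates, 140 per arm and a chi-squared test without continuity correction; a corrected test, which the plan does not specify, would give 63.7% and 74.3% for the DAS28 test alone. Where the gain falls in the range depends on HAQ-DI, ACR50 and CDAI effects that the documents do not give. It is near zero if q2w rarely wins CDAI remission. The lack of per-regimen power in Section 9.1 is a separate reporting gap and is worth closing whether or not alpha is passed.

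**What to change.** Keep the equal split and the endpoint order. Before unblinding, add to Section 9.4.6 and the synopsis:

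> If all five null hypotheses for one regimen are rejected, its 0.0125 passes to the other regimen, whose sequence is re-tested from its first non-rejected hypothesis at one-sided 0.025 (Bonferroni-based graphical procedure).

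Add to Sections 9.4.7 and 9.4.8:

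> For any hypothesis tested at one-sided 0.025, the 95% two-sided interval is also reported.

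In Section 9.1, state power for each regimen on ACR20 and DAS28 (CRP) <3.2 beside the disjunctive figures. Put the testing graph in the SAP.

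The cost is these sentences and one figure, with no extra subjects. The report should note that a result won only through passed alpha will have a 97.5% interval that includes zero, and that occasionally the 95% Newcombe interval will include it too.
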